4.8. Final Analyses

The final EoS analysis will be conducted after the completion of the study (i.e., when all participants complete the Follow-Up period on Day 39 visit) and final datasets authorization. At the EoS analysis all primary, secondary and exploratory objectives will be evaluated with two exceptions: the analysis of (i) viral resistance and (ii) pharmacogenetics (if done), may be evaluated at a later stage and each of these outcomes will be reported separately.

4.9. Changes to Protocol Defined Analyses

There were no changes or deviations to the originally planned statistical analyses specified in the protocol (Dated: 08 May 2023).

The term “partial” dose used in protocol Section 9 was updated with “incorrect” dose in the definition of Estimands and Analysis Sets as it became apparent that it is possible a participant to receive lower (i.e. partial) or higher dose at an administration visit. This does not affect the planned analyses specified in the protocol but provides further clarity for programming work.

5. SAMPLE SIZE DETERMINATION

The sample size is based on feasibility and no formal calculation of power or sample size has been performed.

Further details on sample size considerations are included in protocol Section 6.1.

6. SUPPORTING DOCUMENTATION

6.1. Appendix 1 Study Population Analyses

The study population analyses will be based on the Safety analysis set, unless otherwise specified.

Study population analyses including analyses of participant's disposition, protocol deviations, demographic and baseline characteristics, prior and concomitant medications, will be based on GSK Core Data Standards. Details of the planned displays are included in the OPS.

6.1.1. Participant Disposition

A summary of the number and percentage of participants who enrolled or failed screening will be provided. For screen failures, number and percentage of participants overall and by screen failure reason will be also provided.

A summary of the number and percentage of participants who entered, completed, are ongoing or withdrew from study at each study period (i.e. Monotherapy, Follow-Up) will be provided. A participant will be considered to have completed the Monotherapy period if has completed Day 11 visit and has not started SoC prior to Day 11. If a participant has started SoC treatment prior to Day 11 visit and has performed Day 11 visit, he/she will be classified as 'Not Completed' the Monotherapy phase. A participant is considered to have entered the Follow-Up period if there is a recorded concomitant antiretroviral treatment start date.

A summary of the number and percentage of participants who completed the study as well as those who prematurely withdrew from study will be provided. Reasons for study withdrawal will be summarized. A participant is considered to have completed the study if he/she has a "Completed" status in the Study Conclusion eCRF page.

For treatment arms where more than one study treatment administration is used during the monotherapy period (e.g. in Part 1b), a summary of study intervention status will be provided. This display will show the number and percentage of participants who have completed the scheduled study intervention or have discontinued study intervention prematurely, as well as primary reasons for discontinuation of study intervention.

The number and percentage of participants who withdrew from study due to an AE will be summarised by the outcome (fatal versus non-fatal) of the AE.

A listing of reasons for study treatment discontinuation and a listing of reasons for study withdrawal will be provided.

Subject-level disposition information will be available via [\[REDACTED\]](#).

6.1.2. Demographic and Baseline Characteristics

The demographic characteristics including age, gender, ethnicity, race, height, weight and BMI at baseline will be summarized with descriptive statistics. In addition, the following

age categories will be summarized: 18-64, 65-84 and >=85 based on the Enrolled Analysis Set.

Demographic data will be listed.

Other baseline characteristics data such as medical history, CDC HIV-1 classification will be available at participant-level via [REDACTED]. Participant-level HIV-1 associated conditions and pregnancy data will also be available via [REDACTED]

6.1.3. Protocol Deviations

Important protocol deviations will be summarized and listed.

Protocol deviations will be tracked by the study team throughout the conduct of the study in accordance with the Protocol Deviation Management Plan. These protocol deviations will be reviewed to identify those considered as important as follows:

Data will be reviewed prior to unblinding and freezing the database to ensure all important deviations (where possible without knowing the study intervention details) are captured and categorised in the protocol deviations dataset.

This dataset will be the basis for the summaries of important protocol deviations.

Protocol deviations which result in exclusion from the Per Protocol analysis set will be available at participant level via [REDACTED]

Data will be reviewed prior to unblinding and freezing the database to ensure all deviations leading to analysis population exclusions are captured and categorised in the protocol deviations ADaM dataset (note these exclusions are not captured in the SDTM dataset).

6.1.4. Prior and Concomitant Medications

Prior and concomitant medications will be coded using both the GSK Drug and WHO Drug dictionaries. A listing of concomitant medications based on GSK Drug dictionary will be produced.

6.1.5. Medical Conditions

Medical occurrences beginning after obtaining informed consent but before the start of study intervention will be recorded as medical history/current medical conditions, not as AEs, and will be available via [REDACTED].

6.2. Appendix 2 Data Derivations Rule

6.2.1. Criteria for Potential Clinical Importance

Reference ranges for all laboratory parameters collected throughout the study are provided by the laboratory. A laboratory value that is outside the reference range is considered either high abnormal (value above the upper limit of the reference range) or low abnormal (value below the lower limit of the reference range). A high or low abnormal laboratory value is not necessarily of clinical concern.

The Division of AIDS (DAIDS) grading for severity of laboratory toxicities and clinical adverse events, version 2.1, July 2017 will be used to assign grades to laboratory values as specified in Section 10.7 of the protocol.

In addition, if needed, the following criteria will be used to flag potential clinical importance:

CCI

CCI

6.2.2. Study Period

Assessments and events will be classified according to the time of occurrence relative to the study intervention period.

Pre-Treatment is defined as time prior to the first dose of study intervention.

Monotherapy is defined as time from first study intervention dose (typically Day 1) to start of SoC treatment (typically Day 11).

- If time of assessment or time of study intervention is not collected, Day 1 assessments other than AEs are considered to have occurred prior to study intervention dose and therefore considered on Pre-Intervention period, whereas AEs with Day 1 onset are considered to have occurred after study intervention dose and therefore considered on Monotherapy period.

Follow-Up is defined as time from first dose of SoC treatment until study completion or withdrawal

- If time of assessment or time of SoC initiation is not collected, Day 11 assessments other than AEs are considered to have occurred prior to SoC initiation and therefore considered on Monotherapy period, whereas AEs with Day 11 onset are considered to have occurred after SoC initiation and therefore considered on Follow-Up period.

For concomitant medications, study periods will be defined as follows:

	Pre-Treatment	Monotherapy		Follow-Up		Pre-Treatment	Monotherapy	Follow-Up
(a)	x—x					Y	N	N
(b)	x		x			Y ¹	Y ¹	N
(c)	x			x		Y ²	Y ²	Y ²
(d)		x—x				N	Y ³	N
(e)		x		x		N	Y	Y
(f)				x—x		N	N	Y
(g)	?—x					Y	N	N
(h)	?		x			Y*	Y	N
(i)	?			x		Y*	Y*	Y*
(j)	x			?		Y	Y**	Y**
(k)		x		?		N	Y	Y**
(l)			x	?		N	N	Y
(m)	?			?		Y***	Y***	Y***
(n)	x	x				Y	Y	N
(o)	?	x				Y	Y	N
(p)	x		x			N	Y	N
(q)	x			x		N	Y ⁴	Y
(r)				x	?	N	N	Y**
(s)				x	x	N	N	Y
(t)		x		x		N	Y	Y

x = start/stop date of medication

? = missing start/stop date of medication

* If a medication is stopped during the Monotherapy period or during the Follow-Up period and no start date is recorded it will be assumed that the medication was ongoing from the Pre-Intervention period

** If a medication is started Pre-Intervention or on Monotherapy and no stop date is recorded then usage will be assumed to be ongoing for the remainder of the study

*** If a medication has no start or stop date it will be assumed that the medication was ongoing from the Pre-Intervention period to the Follow-Up period

¹A medication which started before Study Intervention start date and stopped before the SoC start date it will be classified as 'Pre and Monotherapy Treatment'.

²A medication which started before Study Intervention start date and stopped after the SoC start date it will be classified as 'Pre and Monotherapy and Follow-Up Treatment'.

³A medication which started after Study Intervention start date and stopped before the SoC start date it will be classified as "Monotherapy Treatment"

⁴A medication which started on the Study Intervention start date and stopped on the SoC start date it will be classified as "Monotherapy and Follow-Up Treatment"

Similarly, for other cases.

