1.1. Objectives, Estimands and Endpoints

Objectives	Endpoints
Primary	
To evaluate the antiviral activity of orally administered VH4004280 and VH4011499 monotherapy over 10 days in HIV-1 infected Treatment-Naïve (TN) participants	Maximum change from baseline (Day 1) in plasma HIV-1 ribonucleic acid (RNA) through Day 11.
Secondary	
To assess the safety and tolerability of orally administered VH4004280 and VH4011499	
 • Incidence of adverse events (AEs), severity of AEs and AEs leading to study treatment discontinuation • Change from baseline and maximum toxicity grade increase from baseline for liver panel laboratory parameters (consisting of total and direct bilirubin, ALT, ALP and AST)
To characterize the pharmacokinetic profiles of orally administered VH4004280 and VH4011499	PK measures that include but are not limited to: 
 • Maximum observed plasma drug concentration (Cmax), • Time to maximum observed plasma drug concentration (tmax), • Concentrations on Day 11 for VH4004280 and VH4011499
To determine the relationship between the exposure levels of orally administered VH4004280 and VH4011499 and change in plasma HIV-1 RNA	VH4004280 and VH4011499 PK parameters with maximum change in plasma HIV-1 RNA from baseline through Day 11

CCI

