1.1.1. Estimands

Table 1 Estimands Definitions

Endpoints	Estimand			
	Population	Treatment	Summary Measure	Intercurrent event (IE) / strategy / rationale
Primary Objective: To evaluate the antiviral activity of orally administered VH4004280 and VH4011499 monotherapy over 10 days in HIV-1 infected Treatment-Naïve (TN) participants				
Maximum change from baseline (Day 1) in plasma HIV-1 ribonucleic acid (RNA) through Day 11.	Overtly healthy (other than HIV-1 infection) treatment naïve individuals	VH4004280 or placebo single dose on Day 1, or VH4011499 or placebo single dose on Day 1 and Day 6	Mean of maximum change from Baseline in log10 HIV-1 RNA during Days 1-11	
Discontinuation of study treatment due to any reason: Treatment policy strategy, i.e., any HIV-1 RNA data available after study treatment discontinuation day + 1 and prior to starting SoC will be used in calculation of max VLD
 
Use of SoC medication prior to Day 11: While on-treatment strategy, i.e., HIV-1 RNA collected after initiation of SoC, if for any reason this takes place prior to Day 11 will be excluded from calculation of max VLD
 
Use of prohibited medication: Treatment policy strategy, i.e., any HIV-1 RNA data available after use of prohibited medication will be used in calculation of max VLD
 
Missed or incorrect doses of study treatment: Treatment policy strategy, i.e., HIV-1 RNA collected after missed or incorrect dose(s) will be used in calculation of max VLD
 
Rationale: Interest is in evaluating efficacy irrespective of study treatment discontinuation or missed/incorrect doses, or use of prohibited medications, hence a treatment policy strategy is appropriate. Also, interest is to evaluate efficacy of VH4004280/VH4011499 monotherapy and not in combination with

Endpoints	Estimand			
	Population	Treatment	Summary Measure	Intercurrent event (IE) / strategy / rationale
				
other antiretroviral medication hence a while on-treatment strategy is appropriate.
 
Note: discontinuation or missed doses of VH4004280 is not possible as only a single dose on Day 1 is administered, hence these IEs apply only to VH4011499 and to placebo matched for VH4011499.

Secondary Objective: To assess the safety and tolerability of orally administered VH4004280 and VH4011499				

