4. STATISTICAL ANALYSES

4.1. General Considerations

4.1.1. General Methodology

If participants prematurely discontinue the study for non-safety reasons prior to Day 11 (primary endpoint), additional replacement participants may be enrolled at the discretion of the sponsor and investigator. These replacement participants will be assigned to the same treatment sequence and same dose as the corresponding participant who prematurely discontinued from the study. Participants will not be replaced if the reason for discontinuation from the study is due to a safety concern, with the exception of SARS-CoV-2 scenarios (see protocol Section 7.2.1).

Data will be summarized by treatment (i.e., VH4004280, VH4011499, placebo matching VH4004280 and placebo matching VH4011499) and dose level, unless otherwise specified.

Data will be summarized either by visit, or separately for the monotherapy period, the Follow-Up period (i.e. AEs only), and/or overall (i.e., monotherapy period plus Follow-Up period), as appropriate for each endpoint, unless otherwise specified. For summaries focusing on the monotherapy period only (i.e. Day 1 – Day 11), if SoC medication for

any participant starts earlier than Day 11 (for any reason), data collected under SoC will be excluded from the monotherapy period (see respective IE in Estimands Section 1.1.1).

Unless, otherwise specified, summary tables will provide the following descriptive statistics:

- Continuous data: n (number of subjects used for data summary), arithmetic mean, standard deviation (SD), median, interquartile range, minimum and maximum. For PK parameters, geometric mean, SD of log-transformed data and geometric %CV_b may also be used. Confidence interval for the mean or geometric mean may also be used (e.g. check mock outputs in OPS).
- Categorical data: number and percentage of participants in each category.

PK values collected outside analysis visit windows will be excluded from data summaries (applies to both Tables and Figures) but will be included in listings. Figures with subject level information will include all values (i.e. irrespective of being within/outside of analysis visit windows). Confidence intervals for PK data summaries will use 95% confidence levels, unless otherwise specified.

Only lab data from central laboratory will be included in lab data summaries. Lab data from local laboratories, if any, will be included in listings (and flagged appropriately).

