4.2. Primary Endpoint(s) Analyses

4.2.1. Definition of endpoint(s)

Plasma HIV-1 RNA values (copies/mL) will be used for the primary efficacy analysis. Change from baseline at the time point where the HIV-1 RNA is minimum (nadir) during the monotherapy period will be calculated for each participant in the original and log10 scales. The change from baseline at nadir is the primary endpoint used to construct the primary estimand (see Section 1.1.1). According to primary estimand definition (Section 1.1.1), if SoC medication starts prior to Day 11 (for any reason), change from baseline values after SoC initiation will be excluded from calculation of change from baseline at nadir.

Note, the change from baseline at nadir during monotherapy is typically the maximum change from baseline in HIV-1 RNA, or in other words the maximum Viral Load Decline (VLD). However, for participants who have all their post-baseline HIV-1 RNA values during monotherapy higher than the baseline value (e.g. as is the potential with some participants randomized to placebo) the change from baseline at nadir is the minimum change from baseline. Also, if a (placebo) participant has a high increase from baseline in HIV-1 RNA and then a smaller decrease from baseline (or vice versa), the maximum change from baseline is at the point where HIV-1 RNA is its peak (zenith); the change from baseline at nadir will be used in this case in the primary analysis. From now on, in this document by “maximum change from baseline in HIV-1 RNA” during monotherapy we will mean the “change in HIV-1 RNA at nadir”.

The log10 transformation is used to allow for comparisons with data publicly available in the same scale from other compounds, and hence aid in interpretation.

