4.2.2. Main analytical approach

The primary efficacy analysis will be based on the Full Analysis Set.

Maximum change from baseline in plasma HIV-1 RNA during monotherapy will be summarized in original and log10 scale using descriptive statistics as described in Section 4.1.1.

Any missing HIV-1 RNA data (e.g., due to missed visits in the clinic, LFU or for any other reason) will not be imputed and will remain missing. Whatever HIV-1 RNA data are available for a participant during monotherapy and prior to starting SoC will be used to calculate maximum VLD.

Participants who withdraw from study prior to the end of monotherapy period, preventing assessment of primary endpoint, no imputation will be performed for missed assessments after their study withdrawal.

All HIV-1 RNA data from all participants will be included in a listing.

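### SAP 6.2.2 closes the monotherapy period only when SoC starts, which conflicts with the Day 11 limit the SAP sets elsewhere for the primary HIV-1 RNA nadir

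*SAP*

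**What the plan says.** **The derivation chain.** SAP 4.2.1 defines the primary endpoint: "Change from baseline at the time point where the HIV-1 RNA is minimum (nadir) during the monotherapy period will be calculated". SAP 4.2.2 then says which values feed it: "Whatever HIV-1 RNA data are available for a participant during monotherapy and prior to starting SoC will be used to calculate maximum VLD". Neither sentence gives a last day. The period itself is defined in SAP 6.2.2: "Monotherapy is defined as time from first study intervention dose (typically Day 1) to start of SoC treatment (typically Day 11"). Follow-Up begins, in the same section, with the first dose of SoC.

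**The stated window.** SAP 1.1 gives the endpoint as "Maximum change from baseline (Day 1) in plasma HIV-1 ribonucleic acid (RNA) through Day 11". The summary measure in SAP Table 1 is "Mean of maximum change from Baseline in log10 HIV-1 RNA during Days 1-11". SAP 1.2 describes a 10-day monotherapy phase ending at Day 11. SAP 4.1.1 glosses its rule in the same way: "For summaries focusing on the monotherapy period only (i.e. Day 1 – Day 11").

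**SoC timing.** The intercurrent event in Table 1, the sentence in 4.2.1, the rule in 4.1.1 and Per Protocol criterion 05 all concern SoC started before Day 11. No visible rule concerns SoC started later or not at all. Per Protocol criterion 06 is redacted, and criterion 08 is left to adjudication. In the protocol's schedule of activities, the Day 11 visit is fixed with no window, and the first SoC dose is directly observed at its end.

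**The concern.** A nadir depends on how long one looks for it. The estimand looks through Day 11; the derivation rule looks until SoC begins. The two agree when SoC starts on Day 11. Otherwise two programmers could each follow the SAP and obtain different primary values for the same participant.

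The values that could make the difference are scheduled. HIV-1 RNA is drawn on Days 18, 25, 32 and 39 and at early discontinuation, and unscheduled draws are possible. Delay is also conceivable: SoC is locally sourced, Protocol 6.7 acknowledges that access to cART may be slow for some participants, and Protocol Appendix 9 anticipates visits disrupted by COVID-19.

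At stake are the primary mean in arms of six, and the interim reading on about four participants per active arm that informs whether Part 2 is run and at what dose.

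**Working it through.** **Step 1. Trace one value through the rules.** Take a participant sampled on Day 11 who has not started SoC and is sampled again on Day 18.

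| Rule | Does the Day 18 value count toward the nadir? |
|---|---|
| SAP 6.2.2 with 4.2.1 and 4.2.2 | Yes: after first dose, before SoC |
| SAP 1.1, endpoint | No: after Day 11 |
| SAP Table 1, summary measure | No: after Day 11 |
| SAP 4.1.1, monotherapy summaries | No: after Day 11 |
| SAP Table 1, SoC intercurrent event | Silent: covers early SoC only |
| SAP Table 2, visible Per Protocol criteria | Silent: covers early SoC only |
| SAP 6.2.4, Days 12 to 14 exclusion | Not relevant: by-visit summaries only |

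The Per Protocol analysis in SAP 4.2.3 uses all HIV-1 RNA from the monotherapy period, so it inherits the same question.

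**Step 2. Direction.** The minimum of a larger set cannot exceed the minimum of the smaller set it contains. The affected participant's nadir is therefore unchanged or lower.

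**Step 3. Size if RNA keeps falling.** The plan has no figure to reproduce: it tests no hypothesis, sample size rests on feasibility, and the precision table is redacted. The rate of further decline is an assumption, with zero included to cover a plateau or rebound.

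- Extra decline = 7 days (Day 11 to Day 18) × rate.
- Shift in an arm mean from one affected participant = extra decline / n.

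| Assumed rate (log10/day) | Extra decline (log10) | n = 6 | n = 4 (interim) | Placebo, n = 2 |
|---|---|---|---|---|
| 0 | 0 | 0 | 0 | 0 |
| 0.05 | 0.35 | 0.06 | 0.09 | 0.18 |
| 0.15 | 1.05 | 0.18 | 0.26 | 0.53 |

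The interim column applies only if the later draw is available at the data cut. The placebo column is arithmetic for the two-person group in Part 1; the documents give no reason to expect a sustained fall on placebo.

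**Step 4. Size from noise alone.** The schedule has 6 post-baseline draws through Day 11 (Days 2, 3–5, 6, 7, 8–10 and 11). One later draw makes 7; all four visits to Day 39 make 10. For independent normal values, the expected minimum is −1.267 SD for 6, −1.352 SD for 7 and −1.539 SD for 10. With an assumed within-person SD of 0.2 log10:

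- 7 against 6 draws: (1.352 − 1.267) × 0.2 = 0.017, about 0.02 log10.
- 10 against 6 draws: (1.539 − 1.267) × 0.2 = 0.054, about 0.05 log10.

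These are shifts for the one participant. Divided by 6 they are 0.003 to 0.009 log10; divided by 2, 0.009 to 0.027 log10.

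**Step 5. SoC started on Day 11.** No later value is eligible under either rule, and the shift is zero.

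**The case against.** The strongest reply is that the SAP does bound the window, in four places. SAP 4.2.2 sends the primary summary to 4.1.1, which carries the Day 11 gloss, and 4.2.1 ties the nadir to the estimand in 1.1.1. On that reading, 6.2.2 is a general sorting rule that was never meant to redefine the endpoint. This stands against any inference that the SAP as a whole lacks a Day 11 limit: it has one, and the defect is a conflict. It does not remove the conflict, because 6.2.2 is the SAP's operational definition of the period on which 4.2.1 and 4.2.2 rely, and nothing says which text governs.

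A reader might also infer from SAP 6.1.1 that monotherapy never closes for someone who takes no SoC: "A participant is considered to have entered the Follow-Up period if there is a recorded concomitant antiretroviral treatment start date". That goes too far. The same section counts monotherapy as completed once the Day 11 visit is done without earlier SoC.

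A third tempting inference is that the error always favours activity. It does not. A deeper placebo nadir narrows the active–placebo contrast, and in a two-person group one participant carries half the mean.

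It is also fair to say that the trigger departs from the schedule, that inclusion criterion 9 requires participants to be willing and able to start cART on Day 11, and that the redacted criterion 06 or the discretionary criterion 08 might catch late SoC in the Per Protocol set. Criterion 03 may catch a Day 11 sample that slips to a later day. The analysis is descriptive, by-visit summaries keep Day 11 separate, and all HIV-1 RNA values are listed, so a late nadir could be seen. These points limit likelihood and consequence. None settles which value enters the primary Full Analysis Set summary.

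**Conclusion.** The point holds as an internal inconsistency. The derivation rule in SAP 6.2.2, applied through 4.2.1 and 4.2.2, can admit a primary value that the SAP's own endpoint and estimand exclude. It arises only when a pre-SoC HIV-1 RNA value exists after Day 11.

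The documents do not establish the size. It is zero with SoC on Day 11, and the part due to true decline is zero if RNA plateaus or rebounds. Otherwise one affected participant moves a six-person mean by up to about 0.18 log10, assuming a further fall of at most 0.15 log10 per day to a Day 18 draw; noise alone contributes far less. How many participants would start SoC late is also unknown. The correction is worth making because the rule as written can contradict the estimand and the remedy is small.

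**What to change.** In SAP 4.2.1, define the primary nadir as the lowest post-baseline HIV-1 RNA through Study Day 11 and before the first SoC dose. Add the same limit to 6.2.2 for HIV-1 RNA. Leave the AE periods as they are, since an open end at SoC start can serve a purpose there.

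The cost is one sentence of SAP wording and one programming condition. No protocol amendment is needed, because the change enforces the existing estimand. The downside is that a sample intended for Day 11 but taken later, still before SoC, no longer counts toward the nadir. It remains in the listing, and the SAP should say so.
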